## **6. How the Sample Size is Determined:**

- Power, effect-sizes, and retention rates from [name]'s previous EEG investigations were used to estimate samples sizes. we conducted two power analyses using G\*Power (Faul, Erdfelder, Buchner, & Lang, 2009).
- First, assuming a repeated-measures ANOVA with within-subject factors of character label (individual label, generic label, control) and between-subject factors of age(6-, 9-, 12-months) and a medium effect size of  $d = 0.3$  and power of .80 each group should consist of at least 39 participants. Second, for regression analyses, the power analysis was focused on whether parent infant joint attention scores predicted infant learning (as measured by ssVEP power).
- With a medium effect size of  $f^2 = .15$  (Cohen, 1988) and power of .80, the sample should include 55 subjects.
- Given that we plan to collapse across age for this analysis, our estimated sample size of 60 per age group should be sufficient. In addition, we expect a 70% retention rate based on previous cross-sectional infant EEG investigations conducted in [name]'s laboratory and so recruiting 60 per age groups should allow for both analyses to be well powered.

---

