## 9. Possible Discomforts and Risks:

- Only minimal risk inherent in standard clinical procedures for recording EEG in humans and using eye-tracking methods are involved in the proposed studies. All electrical equipment involved is approved for clinical research use and has been installed with attention to proper grounding. The electrode application procedures have not resulted in any known significant damage to skin. The only possible discomforts are sensitivity or allergic reaction to the saline solution (itchiness: occurs very rarely <1%), pink marks on the skin after the snug-fitting net is removed, and a small amount of conducting solution remaining in the hair until rinsed.
- Due to the length of some of the EEG and eye-tracking sessions (approximately 45 minutes to 1-hour total for infant participants), there is a risk of participant fatigue. However, we offer several breaks during each session, participants are closely monitored, and participation in any one component of the experiment takes between 5-15 minutes. If infants become consistently fussy, we will end the testing session.
- Due to the flickering nature of the stimuli there is a potential risk for individuals with Photo Sensitive Epilepsy (PSE). PSE is a form of epilepsy in which seizures are triggered by visual stimuli that form patterns in time or space, such as flashing lights, bold, regular patterns, or regular moving patterns. If anyone in the participant's immediate family has a history of seizures or PSE, this may be an applicable potential risk. To reduce the risk of seizures, we will ask all participants whether or not they have a history of PSE and we will not test those who report having such medical history.
- Psychological risks are also minimal since no pressure or stress is applied at any time. Participants will be given several breaks and are free to discontinue participation at any time.

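### The only model named for the label-by-age comparison, a repeated-measures ANOVA, cannot use infants with one or two usable label conditions; a linear mixed model can, at almost no cost.

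*Protocol*

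**What the plan says.** Protocol section 6 bases the first of its two power analyses on a model described as "assuming a repeated-measures ANOVA with within-subject factors of character label" with three levels, and "between-subject factors of age(6-, 9-, 12-months"). It concludes that at a "power of .80 each group should consist of at least 39 participants". The second analysis is a regression of infant learning on joint attention, collapsed over age, for which "the sample should include 55 subjects". On losses it writes that "we expect a 70% retention rate based on previous cross-sectional infant EEG investigations", and that "recruiting 60 per age groups should allow for both analyses to be well powered". The ANOVA is therefore one of the two analyses that the sample size is meant to serve, and the only method named for the label and age question of Specific Aim 2.

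Section 3 makes label a within-infant factor on both days: six book characters, two per label type, and then EEG trials by label type. It provides for breaks or for stopping the test when an infant fusses. It also allows an additional visit if an infant dislikes the net or is too tired to finish. Section 9 adds: "If infants become consistently fussy, we will end the testing session".

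**The concern.** A classical repeated-measures ANOVA needs a value in every cell of the within-subject factor. An infant stopped partway through may have usable data for one or two label types. Such an infant contributes nothing to the ANOVA, although two observed conditions carry direct information on one label contrast.

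Two things are at stake. The first is precision, since data already collected would go unused. The second is the assumption about the missing data. The complete-case analysis generally needs the infants it keeps to be, within age group, a random subset with respect to the outcome. A likelihood-based mixed model needs only the weaker missing-at-random condition. Loss through fussiness could well depend on how the infant responded to the conditions already seen.

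**Working it through.** **Inputs from the protocol.** Section 6 gives 39 required per age group, 60 recruited per age group, 70% retention, and 55 required for the regression. Section 8 gives 60 dyads at each of three ages, 180 in all.

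**Inputs assumed, because the protocol gives none.** These are the pattern of loss over conditions, the correlation between an infant's conditions (rho 0.5, with 0.3 and 0.7 as a range), and equal variances (set to 1).

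**1. The plan's own figures.**
- Loss allowance: 39 / (1 - 0.30) = 55.7, so 56 per group; 60 are recruited.
- Expected after loss: 60 x 0.70 = 42 per group against 39. Over the three ages, 180 x 0.70 = 126 against 55.
- The regression figure of 55 reproduces exactly with one predictor and alpha 0.05.
- The 39 cannot be reproduced uniquely, because alpha, the correlation and the effect tested are not stated. It is taken here as given.

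The 30% loss is thus already budgeted.

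**2. Complete cases against all available data, rho 0.5.** The variance of a pairwise label contrast is 2 / J, where J is the total contrast information. With three conditions correlated at 0.5, generalised least squares gives these contributions per infant, averaged over which conditions are present:
- all three conditions: 2
- two conditions: 10/9
- one condition: 1/3

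In every scenario 126 infants are complete, so the ANOVA has J = 126 x 2 = 252 and variance 2 / 252 = 0.0079. The other 54 infants differ by scenario.

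*Whole-infant loss.* None of the 54 has usable data. J stays at 252, the ratio is 1.00, and there is no gain.

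*Half of the lost infants lose one condition only.* There are 27 infants with two conditions and 27 with none.
- J = 252 + 27 x 10/9 = 282.
- Variance ratio 282 / 252 = 1.12.
- Standard error smaller by 1 - 1/sqrt(1.119), about 5%.

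*Conditions fail independently, 70% complete.*
- q = 0.70^(1/3) = 0.888 is the chance that a condition is usable.
- Infants with exactly two: 180 x 3q²(1 - q) = 47.7.
- Infants with exactly one: 180 x 3q(1 - q)² = 6.0.
- Infants with none: 180 x (1 - q)³ = 0.25.
- Condition cells used: 3 x 0.888 x 180 = 479, against 3 x 126 = 378.
- J = 252 + 47.7 x 10/9 + 6.0 x 1/3 = 307.
- Variance ratio 307 / 252 = 1.22.
- Standard error smaller by 1 - 1/sqrt(1.218), about 9%.

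Over rho 0.3 to 0.7 the two non-trivial ratios run from 1.23 to 1.21 and from 1.13 to 1.11, so the assumed correlation hardly matters. The loss pattern does.

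**3. If the 70% does not already count infants with a missing condition.** The margin is 42 - 39 = 3 infants per group, or 3/42 = 7.1%. With independent loss per condition it is used up at 1 - (39/42)^(1/3) = 2.4%. At 5% per condition, 42 x 0.95³ = 36 complete cases remain; at 10%, 42 x 0.90³ = 31. Falling below 39 would not by itself be serious. At alpha 0.05 and rho 0.5, interaction power at 36 per group is about 1.00 if the stated effect of 0.3 is read as Cohen's f, and 0.87 if it is read as d, so that f = 0.15.

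**The case against.** **The ANOVA is not fixed as the final analysis.** It appears as the assumption of a power calculation. The protocol has no complete-case rule, and model and missing-data detail is commonly left to a statistical analysis plan, which is not at hand. This stands: a reader might infer that a complete-case ANOVA is the committed analysis, and the text does not say so. Still, section 6 counts it among the analyses to be well powered and names no other for the label question. The point is about the model named, not about missing detail.

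**The 70% is retention of infants, not of conditions.** This also stands. A reader might infer that 30% of infants will have partial data that the ANOVA throws away. Nothing in the protocol supports that. The independent-loss scenario leaves only 0.25 of 180 infants with no data at all, which fits poorly with a retention rate, so 9% marks the favourable end of the scenarios and is not an estimate.

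**Early stopping need not remove a condition.** The order of presentation is not given. If label types are interleaved, a short session leaves fewer trials per condition and no empty cell. Breaks and a possible extra visit also reduce loss. This stands as a reason why the gain may be small.

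**Power loss on both primary outcomes.** A reader might infer this, but the retention figure comes from EEG studies and no loss rate is given for the Day 1 visual fixation outcome.

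**Bias.** A reader might also expect a mixed model to cure selection towards calm infants. It does not recover infants with no data, and it does not remove selection that depends on unobserved attention.

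**Character variation.** One might want to add a random effect for character. With six characters, two per label, and no statement that they rotate across labels, character may be nested in label. Such a term is then a debatable trade-off and is not part of this point.

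**Conclusion.** The point holds as a recommended improvement. The one model named for the label-by-age comparison cannot use infants with incomplete label conditions, in a study that allows sessions to end early, and a model that can use them is readily available. The gain in the standard error of a pairwise label contrast runs from 0% to about 9% over the scenarios examined, with about 5% in the middle one. These figures rest on assumed loss patterns, 126 complete infants of 180, and a common correlation near 0.5. No power shortfall follows from the protocol's own numbers, and the share of infants with partial data is unknown. If there are no partial data, the two models give essentially the same answer, so little is risked by the change.

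**What to change.** State as the primary label-by-age analysis a linear mixed model with fixed effects for label, age group and label-by-age, and a random intercept for infant. Include every infant with at least one usable label condition. Keep the complete-case repeated-measures ANOVA as a sensitivity analysis. If a statistical analysis plan already specifies such a model, align section 6 with it.

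The cost is about one sentence of text and no additional participants; the sample size is unchanged. The small downside is that the model relies on missing-at-random and on a stated covariance form (a random intercept implies equal variances and equal correlations over the three labels). It would help to report, by age group, how many infants have three, two, one and no usable conditions, so that readers can see how much the choice mattered.

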book) and unfamiliar characters including the following: 1) Individual-labels: familiar vs. unfamiliar; 2) Category/generic labels: familiar vs. unfamiliar; 3) No labels: familiar vs. unfamiliar

- **Day 2:** For a second EEG recording, we will measure both parent and infant EEG. This time we will be looking for EEG synchrony between the parent and infant by using a similar ssVEP frequency tagging task as above, now using a phase-locking index.
- To record brain electrical activity, a net with recording sensors is placed on the infant's head. In order to help the electrodes accurately measure the infant's brain activity, we will soak this sensor net in an electrolyte solution. The solution contains distilled water, potassium chloride (salt), and baby shampoo. Recording EEG simply picks up the brain activity that is naturally emitted from the scalp and is non-invasive. If the infant does not like wearing the net or is too tired to complete all of these tasks, the family may be asked to return to the laboratory for an additional visit.
- Outcome measures and time frame:

| Type      | Name                            | Time Frame                                      | Brief Description  |
|-----------|---------------------------------|---|--|
| Primary   | Infant Visual Fixations         | On Day 1  | Infant visual fixations will be recorded during shared book reading and duration of attention and joint attention calculated. Three age groups will be examined (6, 9, 12, month olds).                                      |
| Secondary | Parent Visual Fixations         | when their infant is 6-, 9-, 12-months on day 1 | In the lab, parent visual attention will be measured across conditions using a head mounted eye-tracker. Duration of joint attention within a spatial window will be calculated in conjunction with infant visual fixations. |
| Primary   | Infant EEG power                | On Day 2  | Infant EEG power will be measured and compared across conditions and ages.   |
| Secondary | Infant and parent EEG synchrony | On Day 2  | Infant and parent EEG synchrony will be quantified and compared across conditions.   |

- During the study, the parent will be present and near the infant at all times during each session. If the infant fusses or cries and does not wish to look at the pictures and/or read the book, we will take breaks or stop the test. If, at any point or for any reason, the participant family wishes to stop the test they may advise us to stop

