**8. Describe How Participant(s) Will Be Recruited:**

- We will advertise on UF websites ([name]'s Lab and the Department of Psychology Websites) and in local newspapers.
- Flyers and brochures will be posted in approved locations in local daycares, hospitals, clinics, birthing centers, libraries, churches, and family centers.
- [name]'s lab group will recruit by setting up informational tables and child-friendly actives (brain coloring) at local libraries, museums, and events.
- [name]'s lab will work with local community groups, including the Ounce of Prevention Fund of Florida, Florida Health Babies of Alachua County, and the Southwest Advocacy Group (Gainesville, FL), to recruit additional families from unrepresented groups. We will post fliers and brochures, have information tables at community events, and work with community group staff to identify additional recruitment avenues. We will contact these local groups and when they have a community event, we will set up a table where we hand out our brochures and flyers and ask people if they would like to be contacted to participate in our research. We will have the people who are interested fill out the BCD Lab Database Contact Permission Form, which provides their consent to put them into the database so we can contact them about our study.
- Recruitment will also occur via word of mouth and parents who participate will be asked to let their friends know about our research.
- The BCD Lab Infant Database (IRB#: IRB201601509) will be used to contact families who have already expressed interest in research participation and whose children are the appropriate age for this study.

- We will not begin recruiting or running subjects for this study until the University of Florida has reinstated in-person human research because of COVID-19. Once the university states that we are clear to begin running participants, we will continue our disinfection and cleaning after every participant comes into the lab and continue to wash our hands before and after experimentation.

**Maximum Number of Participants (to be approached with consent): 360 total, including 180 infants and 180 adult parents - 60 dyads at each age (6-, 9-, and 12-months)**

**Amount of Compensation: \$20 plus a small toy (worth \$5), \$10 after each session and the small toy is given at the end of the second session.**

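### The repeated-measures ANOVA is sized on d = 0.3, a two-mean metric, and the effect behind 39 per group is not named, so the power claim is unsupported for the age comparison unless f of about 0.3 was meant

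*Protocol*

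**What the plan says.** Protocol section 6 describes two G*Power calculations.

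- **ANOVA.** The test is a "repeated-measures ANOVA with within-subject factors of character label (individual label, generic label, control) and between-subject factors of age(6-, 9-, 12-months"). The effect is d = 0.3, called medium. The conclusion is "power of .80 each group should consist of at least 39 participants". No alpha, correlation between repeated measures, conversion of d or pattern of means is given, and the effect being powered is not named.
- **Regression** of infant ssVEP power on joint attention. With f² = .15 and the same power, "the sample should include 55 subjects". The pooling over ages applies here only: "Given that we plan to collapse across age for this analysis".

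The section adds that "we expect a 70% retention rate based on previous cross-sectional infant EEG investigations" and closes by saying that "recruiting 60 per age groups should allow for both analyses to be well powered". Section 8 caps recruitment at "60 dyads at each age (6-, 9-, and 12-months").

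Age comparisons are among the stated objectives. The outcome table in section 3 says of a primary outcome: "Infant EEG power will be measured and compared across conditions and ages". Aim 2 in section 2 also asks about differences in attention by age.

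**The concern.** d is a standardised difference between two means. The F-tests for a three-level factor and for its interaction are sized on Cohen's f, which also depends on where the third mean lies. One symbol is therefore being used for a quantity it does not describe.

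In this design the choice of effect matters a great deal. Correlation between an infant's three label conditions raises power for label and label x age but lowers it for the age main effect. The same 39 can be ample for one and well short for another. Because the regression is pooled over age, the ANOVA calculation is the only support in the protocol for any comparison between ages. The closing claim covers that comparison without showing it. What is at stake is how a null age result would be read.

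**Working it through.** **Inputs from the protocol:** k = 3 ages, m = 3 labels, effect 0.3, power 0.80, 39 per group, 60 recruited per group, 70% retention.

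**Assumed:** alpha 0.05, correlation rho between repeated measures (shown over a range), and sphericity (epsilon = 1) unless stated.

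**Formulas** (noncentral F, N = 3n):
- Age: lambda = f² N m / (1 + (m − 1) rho), df 2 and N − 3.
- Label: lambda = f² N m / (1 − rho), df 2 and 2(N − 3).
- Label x age: the same lambda as label, df 4 and 2(N − 3).

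**1. What reproduces.** Regression: f² = 0.15, one tested coefficient, lambda = 0.15 × 55 = 8.25, df 1 and 53. Power is 0.805 at 55 and 0.798 at 54, so 55 is right. Retention: 39 / 0.70 = 55.7, so 56, which is below 60; and 60 × 0.70 = 42, which is above 39.

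**2. Converting d literally.** Suppose d = 0.3 is the gap between the extreme ages.
- Third mean midway: f = d/√6 = 0.122.
- Third mean at one extreme: f = d√2/3 = 0.141.
- The two-group rule f = d/2 = 0.15 is only an upper bound for three groups.

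**3. Power at 42 per group (N = 126).** Age at rho 0.5:
- f = 0.122: lambda = 0.015 × 126 × 3 / 2 = 2.84.
- f = 0.15: lambda = 0.0225 × 126 × 3 / 2 = 4.25.
- f = 0.30: lambda = 0.09 × 126 × 3 / 2 = 17.0.

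| f | age, rho 0 | age, rho 0.5 | label, rho 0.5 | label x age, rho 0.5 | n per group for 0.80 at rho 0.5 (age / label / label x age) |
|---|---|---|---|---|---|
| 0.122 | 0.55 | 0.30 | 0.86 | 0.77 | 144 / 37 / 46 |
| 0.141 | 0.68 | 0.39 | 0.94 | 0.89 | 109 / 28 / 34 |
| 0.15 | 0.73 | 0.43 | 0.97 | 0.92 | 97 / 25 / 31 |
| 0.30 | 1.00 | 0.96 | 1.00 | 1.00 | 25 / 7 / 9 |

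Age lambda falls as rho rises, so the rho 0 column is the best case. On the literal reading, age stays below 0.80 at 42 per group for every rho of 0 or more. Even at the ceiling of 60 per group, age power at rho 0.5 is 0.41, 0.53 and 0.58 for the first three rows. At f = 0.30 the worst case is rho = 1, where lambda = 0.09 × 126 = 11.3 and age power is 0.85.

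**4. Where 39 can come from.** At rho 0.5, none of the rows gives 39. It does appear under particular settings that the protocol does not state:
- f = 0.30, label, Cohen-type lambda = epsilon f² N: 39 at epsilon 0.9 (37 at epsilon 1).
- f = 0.30, multivariate label test with lambda = f² × df2: 39.
- f = 0.30, age: 39 at alpha 0.025 with rho 0.80 to 0.83, or at alpha 0.01 with rho 0.57 to 0.59.
- f = 0.25, age: 39 at rho 0.58 to 0.60.
- f = 0.15: 39 for label at rho about 0.20 and for label x age at rho about 0.36. It is never reached for age, where the smallest n is 49, at rho 0.

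These routes imply different effects and very different age power.

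**5. Smallest age effect detectable at 0.80 with 42 per group:** f = 0.16, 0.20, 0.23 and 0.25 at rho 0, 0.3, 0.5 and 0.7.

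**The case against.** The best defence is that d is a slip for f. The section calls 0.3 medium, and it also calls f² = .15 medium. Read as f, 0.3 gives f² = 0.09; read as d/2, it gives 0.0225, about one-seventh of .15. Benchmarks differ between tests, but on the document's own wording f = 0.3 is the more natural reading. Age is then adequately powered, and 39 can be reached under real software options. Aim 2 is chiefly about labels, and its age clause can be read as label x age. At f = 0.15, rho 0.5 and 42 per group, label and label x age have power 0.97 and 0.92.

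Much of this stands. It rules out three stronger readings that a reader might infer:
- **That the trial is underpowered for age.** This is not shown. With f = 0.3, age power at 42 per group is at least 0.85. The literal conversion also assumes that 0.3 is the largest gap between ages. If it were the step between neighbouring ages, the range would be 0.6 and f = 0.6/√6 = 0.245, above the 0.23 detectable at rho 0.5.
- **That 39 cannot arise if 0.3 was entered as f.** This is false, as step 4 of the working shows.
- **That 39 is a miscalculation.** The inputs are too incomplete to say so.

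What the defence does not remove is that the printed metric is wrong for the test, the powered effect is unnamed, and the outcome table compares primary EEG power across ages as well as conditions.

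**Conclusion.** The point holds in a limited form and should be fixed. Section 6 uses a metric that does not belong to its F-test and does not say which effect 39 refers to, so its inputs do not determine 39. There are two main readings, and each leaves something to correct:
- **d = 0.3 literal, as the gap between extreme ages:** the power claim fails for the age main effect at 42 per group (0.73 at best, 0.30 to 0.43 at rho 0.5). At rho 0.5 it holds for label, and for label x age except at the lowest f (0.77).
- **f = 0.3 meant:** age is adequately powered, but the printed metric is wrong, and G*Power's default form at rho 0.5 gives 25, 7 and 9 per group rather than 39.

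The claim is therefore unsupported for the age comparison unless f = 0.3 or something close to it was intended. Confidence is high on the metric and the unnamed effect. The power figures rest on alpha 0.05, sphericity, the assumed rho and the d-to-f conversion, none of which the protocol states. The regression size and the retention step are correct.

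**What to change.** Keep 60 per age group. In section 6:
1. Restate the ANOVA effect as Cohen's f and, if it came from d, show the pattern of means.
2. Name the effect that 39 refers to (age, label or label x age), with the alpha, rho, epsilon and G*Power effect-size option used, and confirm or correct 39.
3. Replace the closing power claim with achieved power for age, label and label x age at 42 per group for the Day 2 EEG outcome.
4. If d = 0.3 was literal, say that the age main effect is not powered at 80%, and give the smallest detectable age effect (f about 0.16 to 0.25 over rho 0 to 0.7).

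The cost is a wording change and one G*Power rerun, with no added participants. The downside is that the stated power for age may look less favourable.

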## 1. Background:

- Shared book reading during the first year of life has been found to have broad developmental benefits for language (Fletcher & Reese, 2005; Karrass & Braungart-Rieker, 2005; Sénéchal & Young, 2008), socio-emotional development (Bus et al. 1997; Xie, et al., 2018), and cognitive abilities ([name] & Monesson, 2009; 2010; [name], 2011; Pickron et al., 2018; Murray & Egan, 2014).
- Previous research suggests that infants exhibit increased attention and perceptual learning and show more specialized brain responses after parents read them books with specifically labeled (individual-level) names for faces or objects from 6- to 9-months of age (Pickron et al., 2018; [name] & Monesson, 2009; 2010; [name], 2011). However, books with generic category labels or no labels have shown no benefit to infant learning under 9 months old.
- One mechanism that may contribute to infant learning from individual-level labels during shared book reading is joint attention. Joint attention is a foundational skill that develops during the first year of life and is important for social learning and language development (e.g, Brooks & Meltzoff, 2005; Tomasello & Farrar, 1986; Mundy et al., 2007).
- The goal of the present investigation is to determine the extent to which increased parent-infant joint attention during shared book reading and across different labeling conditions leads to increases in infant visual selective attention and parent-infant neural synchrony in 6-, 9-, and 12-month-old infants.

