## **2. Specific Aims:**

- Using both eye-tracking and EEG methods, the goal of the present investigation is to (1) determine the extent to which infant and parent visual attentional coupling during shared book reading predicts later: a) infant selective attention and b) infant and parent neural coupling. Specific aim (2) is to determine the extent to which books with individually-named characters (e.g., “Boris”, “Fiona”) increases parent-infant joint attention and infant selective attention relative to books with generic labels (e.g., “Bear”, “Bear”) or no labels and whether attention differs by age.

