## **3. Research Plan / Study Description:**

- A parent of the participant will first be asked to complete short questionnaires before coming into the lab. Often infants have a limited attention span so we have parents fill out the questionnaire consent form and online Qualtrics questionnaire prior to coming in to the lab so we can expedite their time spent in the lab. This keeps the infant content and not fussy so ultimately, we can get better data when the experiment begins. This questionnaire is designed to provide us with demographic information about who has participated in our studies. These questionnaires include questions regarding their child’s gender, race and ethnicity as well as questions about the demographics of their family (see attached Child and Parent Demographic questionnaires). This information is voluntary and confidential to the extent provided by law.
- **Day 1:** Parents will read a book to their infants in a small in-lab playroom, as they would at home. Prior to reading, infants and their parent will be fitted with a Positive Science head mounted eye-tracker. In addition, both audio and video recordings of the book reading session will be collected using a table-mounted camera. Books with six different characters, one on each of 6 pages will be used during shared book reading. Two of the characters will be labeled with individual level names (e.g., “Boris”, “Anis”), two will be labeled with the same category-level name (e.g., “Cow”) and two will not be labeled. Parents will be seated on the floor with their infant or next to their infant in a high chair. See figure below for outcome measures and time frame for experiments.
- **Day 2:** The participants will return a second day to complete the EEG portion of the experiment. The infant and parent participants will view pictures of faces and/or objects presented with or without sounds while their brain electrical activity (EEG) is recorded in the lab. Here, we employ a “flicker” task and recordings of steady-state visual evoked potentials (ssVEPs) as an index of infant visual selective attention. We will examine the ssVEP power evoked by two overlapping visual objects to quantify the degree of visual attention devoted to learned characters relative to novel characters across labeling conditions. Infants and parents will view ten 6-second trials of two overlapping familiar (from the

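### The regression of infant ssVEP power on joint attention is planned collapsed across age, with no age term, so its slope may mix maturation with the association Aim 1a is about

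*Protocol*

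**What the plan says.** Protocol section 6 describes two analyses. The repeated-measures ANOVA has label as a within-subject factor and carries age as well ("between-subject factors of age(6-, 9-, 12-months"). The second is a regression asking whether joint attention scores predict infant learning, measured by ssVEP power. It is sized at 55 subjects for f² = .15 and power .80. On age, the section says of this regression: "Given that we plan to collapse across age for this analysis, our estimated sample size of 60 per age group should be sufficient". Joint attention is the only predictor named, and no other section adds age as a covariate, stratum or interaction.

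Elsewhere the protocol treats both variables as possibly age-dependent:

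- Section 1: "Joint attention is a foundational skill that develops during the first year of life".
- Section 2, Aim 2, asks "whether attention differs by age".
- Section 3, outcome table: "Infant EEG power will be measured and compared across conditions and ages".

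**The concern.** Aim 1a asks whether attentional coupling during book reading predicts the infant's later selective attention. The sample has three age groups spread over six months of rapid development. If older infants show more joint attention and also a larger ssVEP response, a regression without age finds a positive slope even when, among infants of the same age, the two are unrelated. If the trends run in opposite directions, a real within-age association can be masked.

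The age comparisons planned elsewhere would show whether such trends exist, but they do not adjust this slope. If the wording stays open, the choice between a pooled and an age-adjusted model could be made after the age differences have been seen. The point is confined to Aim 1a.

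**Working it through.** **1. The plan's own figure.** Inputs from section 6: f² = .15, power .80. Alpha is not stated; 0.05 two-sided is assumed. The test of one coefficient uses a noncentral F with λ = f²·N and 1 and N − p − 1 degrees of freedom, where p is the number of predictors.

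- p = 1 (joint attention only): N = 55, power .805.
- p = 3 (joint attention plus two age indicators): N = 55, power .805.

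The stated 55 is reproduced. Because it is the same with and without age, it does not show which model was intended. The evidence is the wording about collapsing and the absence of an age term.

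**2. Sample available.** Section 6 states: "we expect a 70% retention rate based on previous cross-sectional infant EEG investigations". That gives 0.70 × 60 = 42 per age and 3 × 42 = 126 in total. The rate comes from EEG studies, and the regression also needs usable Day 1 eye-tracking from infant and parent. As an assumption, a further 30% loss leaves 0.70 × 42 ≈ 29 per age, or 87.

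**3. Size of the bias.** The protocol gives no age shifts, so a range is assumed. Let joint attention shift by dx and ssVEP power by dy within-age SDs per three-month step, with three equal groups coded −1, 0, 1 (variance 2/3). With within-age correlation ρ and dx = dy = d:

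pooled r = (ρ + 2d²/3) / (1 + 2d²/3)

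With opposite trends of equal size, the numerator becomes ρ − 2d²/3. An f² of .15 corresponds to ρ = √(.15/1.15) = .361.

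- ρ = 0, d = 0.3: .06/1.06 = .057. d = 0.5: .167/1.167 = .143.
- ρ = .361, opposite trends, d = 0.3: (.361 − .06)/1.06 = .284. d = 0.5: (.361 − .167)/1.167 = .167.

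**4. Rejection rates.** From 20,000 simulated trials per scenario, with one joint attention score and one ssVEP value per dyad. The pooled test has N − 2 df; the adjusted test has two age indicators and N − 4 df.

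No within-age association (false positives):

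| dx / dy | Pooled, N = 126 | Pooled, N = 87 | With age |
|---|---|---|---|
| 0.5 / 0 or 0 / 0.5 | 5% | – | about 5% |
| 0.1 / 0.1 | 5% | – | about 5% |
| 0.2 / 0.2 | 6% | 6% | about 5% |
| 0.3 / 0.3 | 10% | 8% | about 5% |
| 0.5 / 0.5 | 36% | 26% | about 5% |

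True within-age f² = .15 (power):

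| dx / dy | Pooled, N = 126 | Pooled, N = 87 |
|---|---|---|
| no trend | .99 | .94 |
| 0.5 / 0 or 0 / 0.5 | .97 | – |
| 0.2 / −0.2 | .97 | – |
| 0.3 / −0.3 | .90 | .77 |
| 0.5 / −0.5 | .45 | .32 |
| any of these, age in the model | .99 | .93 |

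**5. Cost of adjusting.** This depends on what the .15 describes.

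- If it is the age-adjusted effect, the required N stays 55. By noncentral F, power is .991 at 126 and .946 at 87 (joint attention treated as fixed, hence slightly above the simulated .93).
- If it is the pooled effect and only joint attention has an age trend of its own, adjusted f² = .15/(1 + 2d²/3). This is .1415 at d = 0.3 (N = 58) and .1286 at d = 0.5 (N = 64).
- If it is the pooled effect and both trend equally, within-age r = .361(1 + 2d²/3) − 2d²/3. At 0.3 this is .323, f² = .116, N = 70, with power .97 at 126 and .88 at 87. At 0.5 it is .255, f² = .069, N = 116, with power .83 at 126 and .68 at 87.

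**The case against.** The strongest reply is that the sentence is about numbers, not about the model. Retention leaves 42 per age group, fewer than 55, so the authors had to explain why 60 per group is enough, and pooling the groups is that explanation. Section 6 also says only that the power analysis focused on joint attention, which describes the tested coefficient rather than a full predictor list. Covariates are often left to the SAP, which is not at hand.

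The harm also rests on assumed trends. Section 1 speaks of joint attention as a skill, whereas the measured variable is a duration in one session: "Duration of joint attention within a spatial window will be calculated in conjunction with infant visual fixations". The ssVEP outcome in section 3 is a contrast, the "degree of visual attention devoted to learned characters relative to novel characters", which may remove much of a general maturational shift. Sections 2 and 3 plan to examine age differences; they do not predict them. The largest figures need a 1 SD change in both variables over six months, and nothing in the text supports opposite trends. The simulation also reduces three label conditions to one value per dyad.

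Most of this stands as a limit on size. It does not remove the point. In its ordinary sense, collapsing across a factor means ignoring it, and here it contrasts with an ANOVA in the same section that keeps age. That is a stated choice rather than silence. A relative outcome may weaken an age trend but does not exclude one. If only pooling for sample size was meant, the sentence still needs rewording.

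**Conclusion.** The concern holds, as a minor to moderate point. As written, the plan permits an Aim 1a regression without age, although the protocol itself raises age differences in both variables. The effect is negligible when either variable is flat across ages or both trends are small (up to about 0.2 SD per step). It is modest at 0.3 and serious at 0.5, which is the end of an assumed range and not an expectation. All the rates assume linear trends, equal group sizes and two-sided 5% testing. The stated sample size of 55 is correct for its inputs and is not in dispute. Confidence is medium, because the sentence may have been meant only as pooling for sample size.

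**What to change.** Keep all three ages in one regression and state that age enters as a covariate, either as two group indicators or as exact age in days. If that is already the intention, reword the sentence in section 6 to say that the age groups are pooled for sample size with age in the model. A joint attention by age term is optional and supportive only, since no stated aim asks for it.

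The cost is one sentence and one or two degrees of freedom, with no new data. The authors should also say whether f² = .15 is the age-adjusted or the pooled effect. If adjusted, nothing else changes. If pooled, the adjusted analysis needs more subjects, and should both variables trend at 0.5 SD per step, the requirement of 116 leaves little margin at 126 completers and none at 87.
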